16.1 Security and Confidentiality

The data center coordinates the network infrastructure and security with the Health Sciences Campus (HSC) information systems at the University of Utah. This provides us with effective firewall hardware, automatic network intrusion detection, and the expertise of dedicated security experts working at the University. Network equipment includes four high-speed switches. User authentication is centralized with two Windows 2012 domain servers. Communication over public networks is encrypted with virtual point-to-point sessions using transport layer security (TLS) or virtual private network (VPN) technologies, both of which provide at least 128 bit encryption. All of our Web-based systems use the TLS protocol to transmit data securely over the Internet. Direct access to data center machines is only available while physically located inside our offices, or via a VPN client.

All network traffic is monitored for intrusion attempts, security scans are regularly run against our servers, and our IT staff is notified of intrusion alerts. Security is maintained with Windows 2012 user/group domain-level security. Users are required to change their passwords every 90 days, and workstations time out after 5 minutes of inactivity. All files are protected at group and user levels; database security is handled in a similar manner with group-level access to databases, tables, and views in Microsoft SQL Server. Finally, all laptop computers in use in the DCC or in the Department of Pediatrics are whole-disk encrypted.

The data center uses control center tools to continuously monitor systems and failure alerts. Environmental and network systems are also monitored to ensure up time. Highly trained system administrators on staff are available to respond in high risk emergency events. All personnel involved with the DCC have signed confidentiality agreements concerning data encountered in the course of their daily work. All personnel (including administrative staff) have received Human Subjects Protection and Health Information Portability and Accountability Act (HIPAA) education. We require all users to sign specific agreements concerning security, confidentiality, and use of our information systems, before access is provided.

1. PREFACE

This Statistical Analysis Plan (SAP) describes the planned analysis and reporting for the Phase I/II Randomized, Double-Masked Placebo-Controlled Study for Determining the Safety of Processed Amniotic Fluid (pAF) Drops after Photorefractive Keratectomy (PRK) Trial. This study is referred to as the “pAF after PRK” trial in the remainder of this document.

This single-center randomized trial assesses the safety and efficacy of using processed pAF in patients following PRK. More specific safety and efficacy objectives are described in this document.

The structure and content of this SAP provides sufficient detail to meet the requirements identified by the FDA and International Conference on Harmonisation of Technical Requirements for Registration of Pharmaceuticals for Human Use (ICH): Guidance on Statistical Principles in Clinical Trials.¹ All work planned and reported for this SAP will follow internationally accepted guidelines, published by the American Statistical Association² and the Royal Statistical Society,³ for statistical practice.

The following documents were reviewed in preparation of this SAP:

- Trial Protocol
- ICH Guidance on Statistical Principles for Clinical Trials.

The reader of this SAP is encouraged to also read the clinical protocol for details on the conduct of this study, and the operational aspects of clinical assessments and timing for completing a patient in this study.

It is possible that, due to updates or identification of errors in specific statistical software discussed below, the exact technical specifications for carrying out a given analysis may be modified. Such modification is considered acceptable as long as the original, prespecified statistical analysis approach is completely followed in the revised technical specifications.

2. PURPOSE OF SAP

The purpose of this SAP is to outline the planned analyses to be completed for the pAF after PRK trial. The planned analyses identified in this SAP will be included in future study abstracts and manuscripts. Also, exploratory analyses not necessarily identified in this SAP may be performed. Any *post hoc*, or unplanned, analyses not explicitly identified in this SAP will be clearly identified as such in any published reports from this study.

This SAP may be updated in response to additional developments, either within or outside the trial. In such circumstances, an updated version number will be assigned to the revised SAP. Previous SAP versions will be archived.

3. STUDY OBJECTIVES AND ENDPOINTS

3.1 Study Objectives

3.1.1 *Primary Objective*

The primary objective of the pAF after PRK trial is to determine the safety of using processed Amniotic Fluid (pAF) in patients following PRK.

3.1.2 *Secondary Objectives*

The secondary objectives of the pAF after PRK trial are the following:

- To determine if pAF hastens re-epithelialization following PRK compared to placebo.
- To determine if pAF reduces post-operative pain following PRK compared to placebo.
- To determine if pAF affects visual outcome following PRK compared to placebo.
- To determine if pAF affects ocular surface staining and corneal regularity following PRK compared to placebo.

3.2 Study Endpoints

3.2.1 *Primary Efficacy Endpoint*

The primary efficacy endpoint of the pAF after PRK trial is the number of calendar days from PRK to complete re-epithelialization, evaluated in all PRK-treated eyes among enrolled patients.

Time to re-epithelialization will be measured from the end of surgery until the date of the exam where complete re-epithelialization is observed. While specific evaluation times will be collected, since the time of surgery and the time of the follow-up exam are dependent upon scheduling, time to re-epithelialization will be analyzed as an integer, being simply the number of calendar days from the day of surgery to the date of the first examination demonstrating complete re-epithelialization.

3.2.1.1 Eligibility for Primary Analysis

The primary endpoint is to be evaluated in all PRK-treated eyes among consented and enrolled patients.

3.2.2 *Secondary Efficacy Endpoint*

The secondary efficacy endpoint of the pAF after PRK trial is uncorrected visual acuity, as assessed in each PRK-treated eye on Study Day 30.

3.2.2.1 Eligibility for Secondary Analysis

The secondary endpoint is to be evaluated in all PRK-treated eyes among consented and enrolled patients.

3.2.3 *Exploratory Endpoints*

Exploratory endpoints of the pAF after PRK trial, and the populations eligible for each tertiary analysis, include:

- i. Dimensions of epithelial defects as assessed on Days 1 to 8 except Day 2
- ii. Pain as assessed on 0-10 point scale on Days 1 to 7
- iii. Uncorrected visual acuity on Day 8 and at 1, 3, 6, and 12 Months
- iv. Best corrected visual acuity at 1, 3, 6, and 12 Months
- v. Ocular surface staining at 1, 3, 6, and 12 Months
- vi. Corneal Regularity via Surface Regularity Index (SRI) at 1, 3, 6, and 12 months

3.2.4 Safety Endpoints

Safety endpoints of the pAF after PRK trial include:

- i. Ocular adverse events, occurring from randomization until end of follow-up
- ii. Ophthalmic Examination Findings
- iii. Need for Rescue Therapy

While adverse events will be collected and survival tracked for all randomized subjects, the population of patients used in key safety analyses will be those randomized patients who received treatment with study agent for at least one study day.

4. STUDY METHODS

4.1 Overall Study Design and Plan

The pAF after PRK trial will randomize approximately 60 eligible and consented patients to post-PRK treatment for 7 days starting on the day of surgery, with pAF or placebo delivered in a double-blind fashion, in a 1:1 ratio. Treatment with the assigned therapy is to commence immediately after surgery, with the patient receiving the first dose prior to leaving the surgery center.

4.2 Selection of Study Population

Patients will be eligible for enrollment if they meet all of the following inclusion criteria:

- A. Patient is at least 21 years of age
- B. Patient is undergoing PRK for visual correction in both eyes
- C. Patient is willing and able to give consent for study participation and comply with study procedures, including follow-up visits.

Additionally, patients must not meet any of the following exclusion criteria:

- D. Any active eye disease, including keratoconus or any other ectatic disorders
- E. Documented uncontrolled diabetes
- F. Known to be pregnant or nursing, or planning to become pregnant during the

study

- G. Severe dry eye as measured by corneal staining
- H. Calculated PRK treatment resulting in residual stromal bed <300 um
- I. History of previous eye surgery or refractive laser procedures
- J. Any active collagen vascular disease; OR
- K. Visual potential less than 20/20 in either study eye.

4.3 Method of Treatment Assignment and Randomization

Randomization to intervention (pAF or placebo drops) will be performed in a 1:1 ratio, without additional stratification. Randomized blocks of varying lengths will be used to generate the randomization scheme. Smaller block lengths will be used preferentially at the beginning of the generated randomization sequence. Specific block length probabilities are not included in this SAP but will be kept on file at the Coordinating Center, in order to limit predictability of subsequent treatment assignments in case of unblinding. Randomization specifics will be as follows:

1. Two sequences of blocks will be generated using blocks of length 2 and/or length 4, so that the total number of randomizations across the two sequences will be sufficient to achieve the number of randomizations expected in the trial (at least 80). The first sequence will preferentially use smaller block lengths.
2. Within each sequence, the blocks will be permuted as necessary to achieve a fully random permutation of blocks.
3. Each block will then be assigned a random permutation of treatments (for block length 2, a sequence of one of each treatment assignment will be permuted; for block length 4, a sequence containing two of each treatment assignment will be randomly permuted).
4. The final randomization sequence for the trial will be the series of assignments in the first sequence, followed by the series of assignments in the second sequence.

Randomization seeds will be selected and recorded, along with all code used to generate the randomizations, to enable reproducibility of the treatment sequence if necessary.

Randomization sequences will be prepared by the pAF after PRK study biostatistician.

4.3.1 *Handling of Incorrect Randomizations in Study Analyses and Reports*

Any patients who are assigned the incorrect treatment will be given the assigned treatment and treated as such in all analyses (recognizing that extremely rare “good faith” errors of this type may occur and that the cause of any such errors must be immediately rectified). Any such violations are to be reported to the DSMB as part of all reports.

4.3.2 *Delivery of Randomization*

The sequence of randomizations will be delivered to designated unblinded personnel at the University of Utah’s Cell Therapy and Regenerative Medicine Program (CTRM), who will transcribe the randomization sequence in order to treatment boxes with a sequential masked ID, each of which contains the assigned treatment (study drug or placebo).

Each patient who is consented, and who successfully receives PRK and is fully eligible for the trial in all respects immediately after surgery, will then receive the next available treatment box, in numerical order. Therefore, in this trial, only patients who actually receive a treatment box after surgery will be considered to have been randomized and eligible for intention to treat analysis.

4.4 Treatment Masking (Blinding)

The pAF after PRK trial is performed in a double-blinded fashion. Patients, as well as surgeons and study personnel at participating centers involved in the patient's treatment and follow-up, will be blinded to the assigned treatment strategy.

While the pAF after PRK biostatistician will be unblinded to treatment assignments, knowledge of arm-specific treatment results will be limited to biostatisticians involved in the interim and final analyses. Moreover, for all interim analyses, such materials will be prepared with (for example) one arm randomly labeled as "Treatment A" and one arm as "Treatment B", with knowledge of arm identities limited to the biostatistician(s) presenting such materials to the Data Safety Monitoring Board (DSMB). The DSMB may request to be unblinded to treatment assignment at any time, including at the time of their initial look at the trial data.

5. SEQUENCE OF PLANNED ANALYSES

5.1 Interim Analyses

5.1.1 Frequency of and Timepoints for Interim Analysis

The pAF after PRK DSMB is a body of investigators not directly affiliated with the trial. The DSMB is primarily charged with the review of available safety data, including but not limited to adverse events reported in the trial. The DSMB is scheduled to meet three times during the trial, at timepoints after initial outcome data (for at least the first 8 days of follow-up) is available for approximately 5, 30, and 60 randomized patients.

The DSMB will also review other data relevant to the conduct of the trial such as enrollment and protocol adherence, during their within-study meetings. The DSMB will, at their discretion, be able to request analyses additional to those described in this SAP, and to request additional data review meetings on an *ad hoc* basis.

At all meetings, the DSMB is to review interim data and make recommendations regarding continuation or modification of the pAF after PRK trial.

5.1.2 Interim Efficacy Analysis

No interim analyses of efficacy are planned in this trial.

5.1.3 Subgroups for Monitoring and Final Analysis

No patient characteristics have been designated for formal assessment of subgroup effect have been identified in this trial. Exploratory analyses of various treatment effects within and across patient subgroups may be performed in this trial; these will be reported as exploratory in all publications.

5.1.4 *Blinding in the Interim Analysis*

As noted above, the number of Coordinating Center biostatisticians who are unblinded to results by treatment arm and identity of treatment arms will be limited as much as possible, while other Coordinating Center personnel shall be blinded to all safety and efficacy data, prior to final analysis or decision to unblind all investigators to study results.

All interim analysis tables and analyses involving treatment arms will have treatment not explicitly identified, but referred to in a coded fashion, for example as “Treatment A” and “Treatment B”, consistently throughout the report presented to the DSMB. The DSMB will have the option of being unblinded to treatment arm identity at any time including at the time of their initial data review.

5.2 *Final Analyses and Reporting*

All final, planned analyses identified in the protocol and in this SAP will be performed only after all randomized patients have completed the trial protocol and results of all significant queries have been resolved. A blinded data review meeting will be held prior to final database lock and completion of the final analyses. In addition, no database may be locked, random code unblinded, or analyses completed until this SAP has been approved.

Any *post hoc*, exploratory analyses completed to support planned study analyses, which were not identified in this SAP, will be documented and reported as such in all study publications.

6. *SAMPLE SIZE DETERMINATION*

Eliacik et al⁴ found a mean time to re-epithelialization of 3.1 ± 0.6 days for the Comfilcon Group and 3.6 ± 0.5 days for the Lotrafilcon Group. We used this 0.5-day difference as an estimate of treatment effect, and considered within-group standard deviations in the range of 0.5 to 0.7 days. Another key parameter in the estimation of statistical power is the intraclass correlation between eyes in the same patient. This correlation was estimated to be in the range of 0.5 to 0.75, as within-patient healing times have been reported to be nonuniform to a modest extent in the study PI’s experience. The table

below shows true treatment differences detectable with 80% and 90% power under different estimates of the variability of re-epithelialization time and intraclass correlation, **assuming that 56 participants (28 participants and therefore 56 eyes in each treatment arm) complete the trial.** These values were calculated⁵ treating the study as a cluster-randomized trial with clusters (each participant's eyes) of size two.

| Assumed Within-Group Standard Deviation of Primary Outcome | Assumed ICC between a Participant's Eyes | Treatment Difference Detectable with 80% Power | Treatment Difference Detectable with 90% Power |
|--|--|--|--|
| 0.5 days | 0.5 | 0.33 days | 0.38 days |
| 0.5 days | 0.6 | 0.34 days | 0.39 days |
| 0.5 days | 0.75 | 0.35 days | 0.41 days |
| 0.6 days | 0.5 | 0.39 days | 0.45 days |
| 0.6 days | 0.6 | 0.41 days | 0.47 days |
| 0.6 days | 0.75 | 0.42 days | 0.49 days |
| 0.7 days | 0.5 | 0.46 days | 0.53 days |
| 0.7 days | 0.6 | 0.47 days | 0.55 days |
| 0.7 days | 0.75 | 0.49 days | 0.57 days |

Based on numerous power estimates (the above and others), a sample size of 56 patients completing the trial, yields acceptable power to find a significant treatment difference, if the true treatment difference is at least 0.5 days for the time to re-epithelialization outcome.

In order to collect additional safety data and allow for a small number of patients being lost to follow-up, the study will enroll a total of 60 participants.

7. ANALYSIS POPULATIONS

The following analysis populations are planned for the pAF after PRK trial:

- **Eligible Population:** The Eligible Population includes all subjects who are screened for eligibility into the trial, and meet the trial inclusion and exclusion criteria. This population, which will be equivalent to all subjects who received a study identification number, will be used for reporting of study flow per CONSORT guidelines.
- **Intention to Treat Population (ITT):** The Intention-to-Treat Population includes all subjects who provide informed consent and who are randomized into the trial, regardless of whether treatment was initiated or adherence to the protocol.
- **Modified Intention to Treat Population (mITT):** The Modified Intention-to-Treat Population includes all subjects in the ITT population

who receive PRK, and who have analyzable primary outcome data for at least one PRK-treated eye.

- **Safety Population:** The Safety Population includes all patients who received PRK, and who receive treatment with at least one drop of study agent during the post-treatment follow-up.
- **Per-Protocol Efficacy:** The PP-Efficacy population includes patients in the ITT population who are verified to meet all study inclusion and exclusion criteria, and who receive the full assignment treatment, as specified in the protocol, throughout the duration of follow-up.

8. GENERAL ISSUES FOR STATISTICAL ANALYSIS

8.1 Analysis Software

Analysis will be performed using SAS® Software version 9.4 or later whenever possible. Other software packages, including R and StatXAct, may be used in instances where a particular specialized procedure is not available in SAS®.

8.2 Methods for Withdrawals, Missing Data, and Outliers

Per the intention-to-treat principle, any subjects who withdraw from the study will have all available data used in the analysis, per outcome-specific analysis strategies specified elsewhere in this SAP. In the unexpected event that a substantial number of subjects are lost to follow-up or otherwise withdrawn, baseline characteristics and available information on components of efficacy outcomes will be reviewed and compared to subjects not withdrawn, to assess empirically if these subjects differ from those remaining in the study for the scheduled treatment and follow-up time.

Outliers will be reviewed for validity. Outliers that are valid (e.g., reports of extremely poor visual acuity during follow-up) will be included in all primary reports from this trial.

8.3 Multicenter Studies

This is designed as a single-center trial.

8.4 Multiple Comparisons and Multiplicity

As there is a single primary efficacy endpoint for this study, adjustment for multiple comparisons will not be required for the primary analysis.

As a single efficacy outcome has been formally designated as the secondary efficacy outcome, adjustment for multiple comparisons will not be required for the secondary efficacy analysis.

No formal adjustment will be made for multiple comparisons in the reporting of treatment differences for exploratory outcomes. Reported analyses of exploratory outcomes will explicitly note that such outcomes are exploratory.

Safety outcomes for this study will be reported using unadjusted *p*-values for each individual comparison. However, all reports of these outcomes, to the DSMB and in published reports, will explicitly note that multiple safety outcomes have been evaluated.

8.5 Planned Subgroups, Interactions, and Covariates

As noted above, there are no prespecified formal efficacy analysis subgroups for the pAF after PRK trial. Exploratory analyses may examine the association of treatment effect with patient characteristics prior to surgery.

As is noted below, the primary analysis of efficacy will not control for any patient characteristics; patient ID will be included in the analysis to model within-patient correlations of outcomes assessed in individual eyes.

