For the primary efficacy outcome, a mixed effects model with time to healing as outcome and assigned treatment arm as a predictor, including a random effect for each patient to model correlation between eyes in the same participant, will be fit to carry out the primary analysis. A two-sided probability value with an alpha level of 0.05 will be used to test the null hypothesis that time to complete re-epithelialization is not different between the two treatment arms. The primary analysis will be performed on an intention to treat basis.

12.2 Analyses for Other Outcomes:

The key secondary efficacy outcome at 30 days will be analyzed (on a logarithmic scale) using a mixed effects ANOVA model as for the primary aim. Exploratory outcomes will be analyzed in appropriate fashion; for example, each patients pain level (worst in either eye) will be examined on each evaluation day and compared between treatment groups for each day, while each patients peak pain level at any time, and number of days until the patient is pain-free, will be compared

between treatment arms. A Statistical Analysis Plan will fully delineate all analyses to be performed, including additional analyses to assess robustness of the primary and secondary efficacy analyses.

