15.4 Protocol Amendments

Any amendments or administrative changes to an IRB approved protocol will not be initiated without submission of an amendment for IRB review and approval. Any amendments to the protocol that significantly affect the safety of subjects, the scope of the investigation, or the scientific quality of the study are required to submit the amendment for FDA review.

16 Data Coordinating Center

The Data Coordinating Center (DCC) in the Department of Pediatrics at the University of Utah School of Medicine provides data coordination and management services for a variety of national research networks. Anchoring these services is a new state-of-the art, energy efficient data center completed in 2013. The data center facility supports more than 1400 users around the world and provides a secure, reliable, enterprise-wide infrastructure for delivering critical DCC systems and services. The new data center was built using high industry standards and energy efficient cooling solutions. The data center is cooled by Rittals LCP inline cooling technology, providing efficiency, redundancy and modularity. Cooling is based upon a hot/cold aisle design that allows for even air distribution with minimal hot spots. The data center electrical power system contains a redundant Mitsubishi uninterruptible power system (UPS) with a diesel backup generator. The data center is protected with a FM200 fire suppression system, early warning smoke detectors and a heat detection warning system to act as a secondary system to the smoke detectors. Security guards are on-site conducting access control and rounds. Entry

into the data center is restricted by card access and layered security measures and controls. The data center and external building access points are monitored with video surveillance.

- In 2011 the data center began a large scale VMware server virtualization deployment. Currently, the data center has virtualized about 99% of its environment. The virtual environment consists of more than 200 virtual servers. The data centers virtualization solution provides key advantages: high availability in the event of hardware failure, virtual servers automatically go back online in a seamless process.
- Flexible infrastructure disk storage, memory and processor capacity can be increased or reallocated at any time.
- Rapid deployment servers can be provisioned on-demand with minimal waiting on hardware or software.

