10. EFFICACY ANALYSES

10.1 Primary Efficacy Variable Analysis

The analysis of the primary study outcome will include the following test of hypothesis:

H_0 : time to re-epithelialization is not different among eyes receiving treatment with pAF after PRK, compared to eyes receiving placebo drops after pRK.

The alternative hypothesis is:

H_1 : time to re-epithelialization is significantly different among eyes receiving treatment with pAF after PRK, compared to eyes receiving placebo drops after pRK.

For testing the primary hypothesis, a mixed effects linear model with time to re-epithelialization (number of calendar days from PRK to time to complete re-epithelialization) for each eye as outcome, and assigned treatment arm as a predictor will be fit using SAS PROC MIXED. This model will additionally include a random effect for each patient (formally included in the model as each patient’s study ID, defined as a CLASS variable) to model correlation between eyes in the same participant. A two-sided probability value with an alpha level of 0.05 will be used to test the null hypothesis that time to re-epithelialization is not different between the two treatment arms. If the probability value is less than 0.05, regardless of the direction of treatment effect, the null hypothesis above will be considered to be rejected.

The primary analysis will be performed on an intention to treat basis.

All eyes with available outcome data will be included in the model. Any eyes that are not completely re-epithelialized by Day 8 will be assigned a value of 9 days to re-epithelialization in the primary analysis. Any eyes for which time to re-epithelialization is not fully known due to missed visits will be assigned the midpoint of the possible time in the primary analysis (for example, a patient not re-epithelialized in either eye on Day 2, who misses visits on Days 3 and 4 but has complete re-epithelialization in both eyes on Day 5, would be treated as having complete re-epithelialization in both eyes on Day 4 in the primary analysis). Eyes of patients who drop out of the study before Day 8, that do not achieve complete re-epithelialization before dropout, will be treated as missing in the primary analysis, but included in robustness analyses described below.

Results of the analysis above will be accompanied by appropriate presentation (e.g., histograms) of the distribution of number of calendar days to complete re-epithelialization among eyes in each treatment arm.

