10.1.1 Robustness Analyses

In this trial, it is possible that some patients may not be fully compliant with the drug administration regimen, some eyes may not achieve complete re-epithelialization by the time of the Day 8 evaluation, and/or that some patients may drop out prior to Day 8 without having achieved complete re-epithelialization in one or both eyes. If any of these circumstances occur, then the following robustness analyses will be carried out:

1. The two treatment arms will be compared by survival analysis approaches. Specifically, the number of calendar days to re-epithelialization will be treated as a time-to-event variable, and any eyes not exhibiting complete re-epithelialization at their final evaluation (including such eyes evaluated on Day 8) will be treated as censored at time of last evaluation. The time to re-epithelialization curves will be compared between the treatment arms using a two-sided log-rank test appropriate for the within-patient clustered nature of the trial data (REF Stedman R et al. A SAS Macro for a clustered logrank test. Computer Methods and Programs in Biomedicine 2011; 104:266-70).
2. The primary analysis, as well as the survival analysis described immediately above, will be carried out as above among evaluable subjects who met all eligibility criteria for the trial and received their assigned treatment (per-protocol efficacy population), if this population differs from the mITT population.

As noted above in this document, in the event that any patients received the incorrect treatment assignment in the circumstances of an isolated “good faith” error, it is proposed that the treatment received be used in the primary reported analysis, although such errors are to be fully disclosed in the publication of trial results.

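### The primary healing-time model uses no covariate, although each eye's defect area at the end of surgery is already collected and could sharpen the estimate at little cost.

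*SAP*

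**What the plan says.** SAP 8.5 says that "the primary analysis of efficacy will not control for any patient characteristics" and that patient ID enters only to model the correlation between a patient's two eyes. SAP 10.1 specifies healing time "for each eye as outcome, and assigned treatment arm as a predictor will be fit using SAS PROC MIXED", with a random patient effect. Protocol 12.1 agrees: "a mixed effects model with time to healing as outcome and assigned treatment arm as a predictor". Randomization is 1:1 and unstratified (SAP 4.3).

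Protocol sections 5 and 7 have the surgeon measure each eye's defect on Day 1 when surgery ends. Horizontal and vertical dimensions are taken in mm and an area is calculated. The SAP uses defect area as an exploratory outcome (10.3.2) but in no model for healing time.

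The robustness analyses in SAP 10.1.1 are a clustered log-rank test and per-protocol repeats. Neither is covariate-adjusted, and both are conditional: "If any of these circumstances occur, then the following robustness analyses will be carried out". SAP 10.3.5, by contrast, does adjust the surface regularity index for its baseline value.

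**The concern.** The endpoint is the time until a measured defect closes, so the size of the defect at the start is the obvious candidate predictor. Neither the unstratified randomization nor the analysis deals with chance imbalance in it. If it is prognostic, leaving it out makes the confidence interval wider than it needs to be. Healing time is the primary efficacy endpoint and the sole basis of the sample size, although the trial's primary objective is safety. The choice also has to be made in advance, because an adjusted analysis added after unblinding would be post hoc.

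**Working it through.** **Inputs.** Effect 0.5 days; SD 0.5 to 0.7 days; correlation between eyes (ICC) 0.5 to 0.75; 28 completers per arm; two-sided alpha 0.05 (Protocol 12.1 and 12.5; SAP 6 and 10.1). R² is the share of within-arm variance in patient-mean healing time explained by defect area. The documents do not give it, so 0 to 0.30 is assumed.

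**1. The plan's own table.** Treatment is assigned per patient, so work on patient means.

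- Variance = SD²(1+ICC)/2. At SD 0.7 and ICC 0.75: 0.49 × 1.75/2 = 0.429.
- SE of the arm difference = √(0.429 × 2/28) = 0.175 days.
- Detectable difference by normal approximation: (1.960 + 0.842) × 0.175 = 0.490 at 80% power and (1.960 + 1.282) × 0.175 = 0.567 at 90%. The plan states 0.49 and 0.57.
- With a t distribution on 110 df, all nine rows agree with the plan to within about 0.005 days.

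**2. Unadjusted power for 0.5 days.** Noncentral t, 54 df. In the least favourable row the noncentrality is 0.5/0.175 = 2.86, which gives 80.1%.

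**3. Adjusted power.** Variance is multiplied by (1 − R²)(1 + 1/52), with 53 df. The factor 1 + 1/52 is the expected cost of chance imbalance in the covariate. At R² = 0.10 in the same row: 0.429 × 0.90 × 1.0192 = 0.393; SE = √(0.393 × 2/28) = 0.168; noncentrality 2.98; power 83.4%.

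| SD (days) | ICC | Unadjusted power | Adjusted power, R² = 0.10 |
|---|---|---|---|
| 0.5 | 0.5 | 98.9% | 99.3% |
| 0.5 | 0.6 | 98.4% | 99.0% |
| 0.5 | 0.75 | 97.5% | 98.4% |
| 0.6 | 0.5 | 94.2% | 95.8% |
| 0.6 | 0.6 | 92.8% | 94.7% |
| 0.6 | 0.75 | 90.5% | 92.7% |
| 0.7 | 0.5 | 85.8% | 88.6% |
| 0.7 | 0.6 | 83.5% | 86.5% |
| 0.7 | 0.75 | 80.1% | 83.4% |

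**4. Range over R².** The ratio of confidence interval widths is √((1 − R²)(1 + 1/52)) × t₅₃/t₅₄, the same in every row.

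| R² | Interval width, adjusted/unadjusted | Adjusted power, SD 0.7, ICC 0.75 (unadjusted 80.1%) |
|---|---|---|
| 0 | 1.010 | 79.3% |
| 0.05 | 0.984 | 81.3% |
| 0.10 | 0.958 | 83.4% |
| 0.20 | 0.903 | 87.4% |
| 0.30 | 0.845 | 91.3% |

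Break-even is at R² of about 0.02. At R² = 0.10 the least favourable row goes from 82.8% to 85.9% with 60 completers and from 84.7% to 87.6% with 63.

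**5. Missing covariate.** Simulated in the least favourable row with R² = 0.10 and 10% of patients lacking the area (20,000 trials per setting). Dropping them gives 79.2% power, below the unadjusted 80.1%. Assigning the overall mean gives 82.9%. Type I error was 4.6% to 5.1% across the missing-data settings.

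**6. Per-eye covariate.** An eye-level mixed model (4,000 trials per setting) with R² = 0.10 per eye went from 79.8% to 83.9% when the two eyes' areas correlated 0.5, and from 81.3% to 84.3% at 0.9 (both correlations assumed).

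**The case against.** The strongest case against is that the plan makes an explicit, consistent and valid choice, and that the benefit rests on an R² found nowhere in the documents. Protocol 3.1 describes the surgical wound as uniform and predictable, and a covariate that varies little explains little. At the SDs of the cited study (0.5 and 0.6) unadjusted power is already 90.5% to 98.9%, and the gain at R² = 0.10 is only 0.4 to 2.2 points. All of this stands. It limits the size of the point but does not remove it, because the possible loss is small and the possible gain is not.

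It is also fair that SAP 10.3.2 already models the change in defect area over time. That analysis is exploratory and does not adjust the healing-time comparison. The SRI precedent is a weaker parallel than it looks, since it adjusts an outcome for its own baseline.

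The order of events is a real gap. Protocol sections 5 and 5.1 put both the measurement and the first drop at the end of surgery and do not say which comes first. Protocol 5.3 randomizes before surgery, whereas SAP 4.3.2 assigns the treatment box afterwards, so the measurement may follow randomization. The surgeon is masked, so bias is unlikely, but new wording cannot establish the order for patients already treated.

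Finally, a simulation that rounded times to whole days gave 76.3% unadjusted power in the least favourable row. Rounding there raised the SD to about 0.74, above the plan's 0.7, which already refers to an integer outcome. The gain from adjustment was about the same (79.2% at R² = 0.10).

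**Conclusion.** The point holds as an improvement in efficiency. It is not a defect: the unadjusted analysis is valid and the plan's power table reproduces. At R² = 0.10 adjustment narrows the interval by 4.2% in every row and adds 0.4 to 3.3 points of power, mostly where the SD is 0.7. At R² = 0.30 the interval narrows by 15.5%. If defect area is unrelated to healing time, the interval is 1.0% wider and at most 0.8 points of power are lost. These figures rest on the assumed R², 28 completers per arm, a linear effect of area, and a measurement unaffected by treatment. The change is worth making, with moderate confidence because the true R² is unknown.

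**What to change.** Decide before database lock, through people who have not seen results by arm. This needs care, because SAP 4.4 leaves the trial biostatistician unblinded to assignments and SAP 5.1.1 schedules DSMB reviews of interim data.

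1. **SAP 8.5 and 10.1:** add each eye's defect area at surgery completion as one linear fixed covariate in the primary model.
2. **Protocol and SAP:** state that this area is measured before the first study drop.
3. **SAP 10.1:** eyes with a healing time but no baseline area are assigned the mean area of all eyes, calculated without regard to arm. This preserves the rule "All eyes with available outcome data will be included in the model".
4. **SAP 10.1.1:** report the current unadjusted model as a supportive analysis.
5. **Protocol 12.1 and 12.2:** align 12.1 with the new model. Because 12.2 analyses visual acuity "using a mixed effects ANOVA model as for the primary aim", state there that the acuity model keeps treatment arm and the random patient effect only.

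The cost is a SAP update and a minor protocol amendment, which under Protocol 15.4 "will not be initiated without submission of an amendment for IRB review and approval". No new data are collected.

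If an amendment is not wanted, keep the unadjusted model as primary and add the adjusted model to SAP 10.1.1 as a robustness analysis that is always run. That needs a SAP update only, since Protocol 12.2 already leaves the SAP to define the analyses, "including additional analyses to assess robustness of the primary and secondary efficacy analyses".
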